5.3 Population characteristics

We will collect demographic information and medical history as provided by patients.

5.4 Statistical Analysis

The primary goal of the analysis is to estimate the diagnostic accuracy of 68Ga-DOTATOC PET-CT for detecting NET compared to conventional imaging techniques. Analyses will be performed with both patient and lesion as the unit of observation. Since all patients are expected to have at least one NET lesion, only sensitivity can be estimated in the analysis by patient, whereas both sensitivity and specificity will be estimated in the lesion based analysis. We will compute the relevant proportions and corresponding 95% confidence intervals, with adjustment for correlated data from the same patient. Results from pathology reports available from previous biopsy or surgical specimens will be considered the gold standard. In the absence of pathology reports, initial and follow up diagnostic CT or MRI scan following nonsurgical therapy including chemotherapy will be considered the gold standard.

Kappa statistics will be computed and McNemar's test will be performed to compare the sensitivity and specificity between ⁶⁸Ga-DOTATOC PET-CT with SPECT and diagnostic CT for detecting NET. All analyses will be performed in SAS and p-values < 0.05 will be considered statistically significant.

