3.0 Inclusion Criteria

- 3.1 Signed informed consent.
- 3.2 Patients of either gender, aged ≥18 years.
- 3.3 Karnofsky status ≥60.
- 3.4 Life expectancy of at least 12 weeks.
- 3.5 Histologically and/or clinically confirmed and/or suspicious of NET.
- 3.6 A diagnostic CT or MRI of the tumour region or suspected area within the previous 4-6 months prior to dosing day is available.
- 3.7 Recent Blood test results up to 4-6 weeks as follows:
 - 3.7.1 WBC: >2*109/L
 - 3.7.2 Haemoglobin: >8.0g/DI
 - 3.7.3 Platelets: >50x10⁹/L
 - 3.87.4 ALT, AST, AP: ≤5 times ULN
 - 3.7.5 Bilirubin: ≤3 times ULN
- 3.8 Serum creatinine: within normal range or <120µmol/L for patients aged 60 years or older.
- 3.9 Negative pregnancy test in women capable of child-bearing.

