5.0 Study design

This is a prospective, Phase 2, single center study in a total of 40 subjects with Neuroendocrine Tumors (NETs). Study participants will receive 68Ga-DOTATOC and undergo a PET/CT imaging study, to investigate its suitability as a PET imaging agent for NETs. The radiation (imaging) dose will be $111-185 \, \text{MBq} (3 - 5 \, \text{mCi}) \pm 25\%$. All doses after labeling will be presented in buffered solution for intravenous injection. Imaging will start 90 $\pm 30 \, \text{minutes}$ after injection.

About 40 patients with histologically and/or clinically confirmed and/or suspected NET are anticipated to be enrolled during 3 years from initiating the study.

Patients will be recruited at Montefiore Medical Park where there is a medical group specialised in the diagnosis and treatment of NETs. Each patient will undergo a screening visit within 14 days prior to receiving study medication.

The primary goal of the analysis is to estimate the diagnostic accuracy of 68Ga-DOTATOC PET-CT for detecting NET compared to conventional imaging techniques.

The patients will be followed up by a telephone call 24 hour after administration of test drug (⁶⁸Ga-DOTATOC) to assess if patients have experienced any adverse event. This information will be captured in the CRF for further assessment.

5.1 Image Acquisition:

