5.2. Interpretation of Data

The number of lesions that could be identified clearly as single focus will be determined for each patient. To enable a methodic and consistent approach to lesion identification, we will create 3 categories of lesion sites: organs (Head and Neck, lungs, breast, liver, pancreas, gastrointestinal tract, kidney, spleen, and pelvis/ovaries), nodal regions (Axillary, thoracic, mesenteric, abdominal, and pelvic [excluding mesenteric], and inguinal regions), and musculoskeletal system (vertebrae, bony thorax, bony pelvis, and limb bones). Because of confluence and inability to clearly delineate single liver lesions in some cases, liver metastases will be classified as 1 organ metastasis, independent of the number of liver metastases present. Lymph nodes smaller than 1 cm on CT or MRI and showing marked avidity for ⁶⁸Ga-DOTATOC will be labeled as positive for

disease. In cases where images from ¹¹¹In-Octreotide are available for comparison, the same imaging parameters will be applied. The presence of lesions will be confirmed by cross-sectional imaging of all patients with CT or MRI. As there may be lesion/s that can show abnormal focal activity on Ga-68 PET images but not on morphologic images, such lesion/s will be considered positive NET.

Each scan (⁶⁸Ga-DOTATOC) will be read by two independent, board certified nuclear medicine physicians blinded to the results of other scan. A third independent nuclear medicine physician will then review both the results (independent reviews) and clinical information to reach to a consensus.

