5.4 Justification of Sample Size

We project that it will be feasible to recruit a total of 40 patients with histologically and/or clinically confirmed and/or suspected NET into the study. Each subject is expected to have on average 2 lesions and among the 80 total lesions; we project that 60% will be positive for NET. To evaluate the adequacy of the sample size (i.e., number of lesions), we computed the precision, as measured by the width of the 95% CI, with which the sensitivity and specificity of 68Ga-DOTATOC PET-CT scan can be estimated. The width of the 95% CI will be no greater than +/-14% for sensitivity and +/- 17% for specificity in the lesion-based analysis. For the patient-based analysis, the precision with which sensitivity can be estimated is +/- 15%.

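### Section 5.4 plans no patient-level specificity because every patient is expected to have NET, but patients only suspected of NET are eligible and nothing says how a NET-free patient is analysed

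*Combined protocol and SAP*

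**What the plan says.** Section 5.4 (Statistical Analysis) analyses accuracy both by patient and by lesion. By lesion, sensitivity and specificity are both planned. By patient, specificity is set aside: "Since all patients are expected to have at least one NET lesion, only sensitivity can be estimated in the analysis by patient".

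The population is described more widely elsewhere. Inclusion criterion 3.5 reads "Histologically and/or clinically confirmed and/or suspicious of NET". Section 5.0 (Study design) says "About 40 patients with histologically and/or clinically confirmed and/or suspected NET are anticipated to be enrolled", and the sample-size section, which is also numbered 5.4, refers to "40 patients with histologically and/or clinically confirmed and/or suspected NET into the study". Section 5.0 also describes the participants simply as subjects with NETs, but this does not alter the eligibility rule.

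The reference standard in 5.4 is pathology where a report exists. Otherwise, "initial and follow up diagnostic CT or MRI scan following nonsurgical therapy including chemotherapy will be considered the gold standard".

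The sample-size section gives one patient-level figure: "For the patient-based analysis, the precision with which sensitivity can be estimated is +/- 15" per cent. It states no denominator rule and gives no figure for patient-level specificity.

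**The concern.** The only reason given for omitting patient-level specificity is that no patient will be free of NET. The eligibility rule does not guarantee this. No section requires NET to be confirmed, caps the number of patients with suspicion only, or says what happens in the by-patient analysis when a patient turns out not to have NET.

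Followed as written, such a patient can be handled in two ways, and neither is satisfactory. If the patient is left out of the by-patient analysis, a positive scan in someone without NET does not appear there. If the patient stays in the sensitivity denominator because everyone was expected to have NET, a false-positive scan counts as a detection and a correctly negative scan counts as a miss. Diagnostic accuracy is the primary goal and the patient is one of its two units of analysis, so the rule should be fixed before results are seen.

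**Working it through.** **1. Reproduce the plan's precision.** The formula is not stated. The worst-case Wald half-width, 1.96 x sqrt(0.25/n), matches all three figures in the sample-size section. The lesion inputs are 80 lesions, 60% NET, so 48 NET and 32 non-NET.

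- Lesion sensitivity, n = 48: 14.1% (stated 14%).
- Lesion specificity, n = 32: 17.3% (stated 17%).
- Patient sensitivity, n = 40: 15.5% (15.495% unrounded; stated 15%).

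The patient-level figure is therefore consistent with all 40 patients being in the sensitivity denominator. This is an inference. If the figure was truncated, n = 39 (15.7%) or n = 38 (15.9%) would fit too, and a Wilson interval at n = 38 gives 15.2%.

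**2. Vary the number of NET-free patients.** The documents give no share. I assume 2 to 8 of 40. For orientation only, the 84-patient DOTATOC study summarised in section 2.3 had 12 true negatives and 1 false positive on PET: 13/84 = 15.5%, or about 6 of 40. Its case mix may differ. The lower exact 95% limit for specificity when all n NET-free patients are PET-negative is 0.025^(1/n).

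| NET-free | NET-present | Sensitivity half-width | Exact 95% CI for specificity, no false positives |
|---|---|---|---|
| 2 | 38 | 15.9% | 16-100% |
| 4 | 36 | 16.3% | 40-100% |
| 6 | 34 | 16.8% | 54-100% |
| 8 | 32 | 17.3% | 63-100% |

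These half-widths are worst case. At 97% sensitivity and n = 32 the half-width is about 6%.

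**3. Show what the missing rule does.** The counts here are assumed: 34 NET-present patients with 33 PET-positive, and 6 NET-free patients with 1 PET-positive.

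- Status set by a reference: sensitivity 33/34 = 97.1%; specificity 5/6 = 83.3% (exact 95% CI 36-99.6%).
- NET-free patients left out: sensitivity 33/34 = 97.1%; the false positive is not shown.
- All 40 treated as NET-present: (33 + 1)/40 = 85.0%; the false positive counts as a hit and the five correct negatives count as misses.

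**4. Allow for an imperfect reference.** Suppose the one PET-positive patient in the NET-free group has negative CT/MRI and no pathology, so that true status is unverified.

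| Counted as | Sensitivity | Specificity |
|---|---|---|
| NET-present | 34/35 = 97.1% | 5/5 |
| NET-absent | 33/34 = 97.1% | 5/6 = 83.3% |
| Excluded | 33/34 = 97.1% | 5/5 |

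PET sensitivity hardly moves, but specificity does. So does the comparison with CT: counted as NET-present, this patient is a CT miss and a discordant pair in favour of PET; under the other two rules the patient does not enter the sensitivity comparison.

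**The case against.** The strongest reply is that the gap is narrow. Lesion-level specificity is planned, so a false-positive focus in a NET-free patient can still be counted there. The wording in 5.4 is an expectation, and recruitment runs through a group specialised in NETs, so NET-free patients may be few. Any specificity estimate would be very imprecise. All of this stands, and it limits the severity. It does not supply a rule for the NET-free patient, and lesion-level specificity does not say how often a patient without NET has a positive scan.

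A second reply concerns the reference. CT/MRI misses NET: in the cited 84-patient study, diagnostic CT was false negative in 26 patients. Setting status from CT/MRI alone would remove NETs seen only on PET from the sensitivity denominator and tilt PET v CT towards CT. This also stands, and the fix has to bracket sensitivity as well as specificity.

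Three stronger readings are tempting, and the documents do not support them.

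- A reader might infer a number of NET-free patients from the projection that "among the 80 total lesions; we project that 60% will be positive for NET". The plan gives two lesions per patient only as an average, and 48 NET lesions among 40 patients leave room for at least one each.
- A reader might infer that section 5.2 turns false-positive patients into true positives, because PET foci without a morphologic correlate are covered by "such lesion/s will be considered positive NET". That rule is written for lesions, and no section carries it over to patient status.
- A reader might infer that the +/-15% is an error. It reproduces on its own inputs.

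**Conclusion.** The point holds as a gap in the by-patient analysis. Section 5.4 excludes patient-level specificity on a premise that the eligibility rule does not secure, and the handling of a NET-free patient is undefined. The consequence is a missing false-positive count by patient, or a sensitivity denominator that includes patients without the disease. Lesion-level specificity is unaffected by this rule.

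Its size depends on a number that the documents do not give. With an assumed 2 to 8 NET-free patients of 40, the effect on stated precision is modest, from 15.5% to between 15.9% and 17.3% in the worst case. The effect on the sensitivity estimate is small if NET-free patients are left out, and could be large if they are kept in (97.1% v 85.0% in the assumed example). If every enrolled patient has NET, nothing changes. I rate it a cheap improvement of low to moderate severity.

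**What to change.** In section 5.4:

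1. Replace the restriction to sensitivity with a patient-level 2x2 table against the reference standard already defined there (pathology, otherwise initial and follow-up CT/MRI). State that the study PET does not set patient status.
2. Compute sensitivity among reference-positive patients. If any patients are reference-negative, report specificity descriptively with an exact 95% CI.
3. List PET-positive patients with negative CT/MRI and no pathology separately as unverified. Show sensitivity (including PET v CT) and specificity with these patients counted as NET-present, as NET-absent, and excluded.
4. In the sample-size section, state that the +/-15% assumes all 40 patients have NET (worst case 15.5%), and that it would be about +/-16% to +/-17% with 38 to 32 NET-present patients.

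The cost is plan wording, one table and a CRF field for the source of each patient's reference status; no extra patients or scans are needed. There are two downsides. The specificity interval will be very wide (6/6 gives 54-100%). Some patients will also remain unclassifiable, because the fallback reference relies on imaging after nonsurgical therapy and the only follow-up contact that section 5.0 schedules is a telephone call at 24 hours. These patients should be listed with their PET result.

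### The negatives for lesion-level specificity are selected by the scans being compared, which tends to favour PET, and the 32 behind the ±17% have no stated source

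*Combined protocol and SAP*

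**What the plan says.** Three parts of the plan bear on this.

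- **Section 5.4, Statistical Analysis.** Because every patient is expected to have disease, the by-patient analysis gives sensitivity only, "whereas both sensitivity and specificity will be estimated in the lesion based analysis". Intervals are to be adjusted for correlation within patients. The reference is existing pathology or, failing that, initial and follow-up CT or MRI. McNemar's test compares sensitivity and specificity with SPECT and with diagnostic CT.
- **Section 5.2, Interpretation of Data.** The unit counted is a focus that can be singled out on a scan. To make lesion identification consistent, "we will create 3 categories of lesion sites" (organs, nodal regions, musculoskeletal), and liver metastases are collapsed to one. Sub-centimetre nodes with marked uptake are labelled positive. Of foci visible on PET without a morphologic counterpart, it says "such lesion/s will be considered positive NET". In-111 images are used where they exist.
- **Section 5.4, Justification of Sample Size.** "Each subject is expected to have on average 2 lesions and among the 80 total lesions", of which "we project that 60% will be positive for NET". From this it concludes: "The width of the 95% CI will be no greater than +/-14% for sensitivity and +/- 17% for specificity in the lesion-based analysis".

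The document nowhere defines a negative lesion, says that a disease-free site counts as a negative, or explains where the non-NET 40% comes from.

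**The concern.** Specificity needs a set of units that are truly free of NET and that enter the analysis whatever the index test shows. Here a unit enters only because a scan displayed it, and one group of PET findings is declared true by rule. The lesion-level figure is the trial's only specificity estimate, so there is no second result to check it against. If the selection leans towards PET, the estimate, its interval and both specificity comparisons lean the same way. If the negatives are fewer than projected, the stated precision is lost as well.

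**Working it through.** **1. The plan's own figure.** Inputs from the sample-size section: 40 patients, 80 lesions, 60% positive. Positives: 80 × 0.60 = 48. Negatives: 80 − 48 = 32 (derived, not printed). The half-width with independent units at the worst case p = 0.5 is 1.96 × √(0.25/n):

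| Quantity | n | Computed | Stated |
|---|---|---|---|
| Lesion sensitivity | 48 | 14.1% | 14% |
| Lesion specificity | 32 | 17.3% | 17% |
| Patient sensitivity | 40 | 15.5% | 15% |

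All three agree to within rounding. The arithmetic is sound, given 32 negatives and no clustering.

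**2. Where a negative can come from.** Applying 5.2 together with the reference in 5.4:

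| Focus | Can the reference call it negative? | PET result if negative |
|---|---|---|
| On PET, nothing on CT/MRI | No, NET by rule | – |
| Node under 1 cm on CT/MRI, marked uptake | No, labelled positive | – |
| Otherwise on CT/MRI, no uptake | Yes | True negative |
| Otherwise on CT/MRI, with uptake | Yes | False positive |
| On SPECT only | Yes | True negative |
| Site clear on every scan | Not counted | – |

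In the McNemar comparison with CT, the pair that counts against PET (PET false positive, CT true negative) requires CT to show a lesion, the CT reading to call it benign, PET to take it up, and the reference to clear it. The pair that counts for PET requires only that CT calls a lesion disease, PET shows no uptake, and the reference clears it. The most direct PET error, uptake with nothing on CT, is moved out of the negatives altogether and counts as disease that CT missed.

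**3. How precision depends on the 32.** The projection needs 32/40 = 0.8 cleared lesions per patient. With fewer, at p = 0.5 and independent:

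- 24 negatives: 20.0%
- 16 negatives: 24.5%
- 8 negatives: 34.6%

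For rough context, the 84-patient comparison of PET, SPECT and CT summarised in section 2.3 had CT false positives in 5 patients, which scales to 5/84 × 40 = 2.4 patients here. That count is per patient and leaves out lesions correctly read as benign, so it does not bound the number of negatives.

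**4. Clustering.** If the 32 negatives fall two to a patient, the design effect is 1 + ICC. Assumed ICCs of 0.3, 0.5 and 1 turn 17.3% into 19.8%, 21.2% and 24.5%.

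**5. The 5.2 site as the unit.** There are 9 organ sites, 4 skeletal sites, and 5 or 6 nodal regions depending on how the nodal list is read: 18 or 19 sites. Assume that every site is evaluable in all 40 patients and that the 48 positive lesions occupy 48 separate sites. Negatives are then 18 × 40 − 48 = 672 or 19 × 40 − 48 = 712, averaging m = 16.8 or 17.8 per patient. With design effect DE = 1 + (m − 1) × ICC, the half-width is 1.96 × √(0.25 × DE/n):

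| Assumed ICC | 18 sites: DE, half-width | 19 sites: DE, half-width |
|---|---|---|
| 0.05 | 1.79, 5.1% | 1.84, 5.0% |
| 0.10 | 2.58, 6.1% | 2.68, 6.0% |
| 0.30 | 5.74, 9.1% | 6.04, 9.0% |

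These are best-case figures; fewer evaluable sites widen them.

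**The case against.** A reader might infer that lesion-level specificity has no valid denominator and that 32 negatives cannot arise. The documents do not support that. A lesion shown by CT, MRI or SPECT and then cleared by pathology or follow-up imaging is a legitimate negative, and section 5.4 supplies a reference able to clear it. Section 3.5 admits patients with only suspected NET, so non-NET lesions are plausible. Thirty-two is unsupported, not impossible.

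A reader might also infer that CT begins every negative as a false positive. That goes too far. CT can display a lesion that is read as benign, a SPECT-only focus can be a CT true negative, and a CT-visible benign lesion without SPECT uptake is a SPECT true negative. What stands is a tilt, not a certainty.

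It can be argued that specificity among candidate lesions is a coherent quantity and that a written definition of a negative lesion would be enough. The quantity is coherent, but a definition alone would leave both the scan-based selection and the PET-only rule in place.

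The best objections are to the remedy. Changing to sites does not by itself remove the PET-only rule. Section 3.6 requires diagnostic CT or MRI only of the tumour region or suspected area, so many sites may have no comparator or reference. In-111 images will not exist for everyone. Site-level and lesion-level specificity are also different quantities, so 5-9% against 17% is not a like-for-like gain. All of this stands, and it sets the limits placed on the fix.

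**Conclusion.** The concern holds in this form: the specificity denominator is selected by the scans under comparison, one class of PET false positive is excluded by a stated rule, and the likely direction of bias is towards PET. The size of that bias cannot be calculated from the documents, because they do not project how many PET-only foci there will be or how many of those would prove not to be NET.

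The ±17% is not an arithmetic error. It is conditional on an unsourced count and on independence, although section 5.4 itself promises adjustment for within-patient correlation. Halving the count to 16 adds about 7 points (24.5% against 17.3%), and a quarter of it doubles the half-width (34.6%). The clustering figures rest on assumed ICCs and on two negatives per affected patient.

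**What to change.** 1. For specificity, make the 5.2 site the unit, and settle whether the list has 18 or 19 sites. Score each site positive or negative for PET, comparator and reference, restricted to sites that the comparator and reference imaging cover, with patient-clustered intervals. The region-based analyses in several studies cited in section 2.3 are a precedent.
2. Set the reference for specificity independently of PET. Do not count a PET-only focus as NET unless pathology or follow-up CT/MRI supports it. Otherwise class it as unverified and show the results with it counted each way.
3. Keep lesion-level sensitivity. Report lesion-level specificity as secondary, with the number of negatives actually observed.
4. Restate the ±17% as conditional on 32 independent negatives. Add a clustered site-level half-width with its assumed ICC and expected number of evaluable sites.

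Cost: a site checklist for the PET reads and for the existing comparator images, plus revised wording in 5.2 and 5.4. Section 5.2 describes a double read only for the DOTATOC scan, so scoring the comparator images by site is some added work. Site-level specificity will run high because many sites are plainly clear, which is why it should appear beside the lesion-level result. This is a cheap improvement.

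### Diagnostic CT is both a comparator and the fallback gold standard, and 5.2 does not say whether an unverified PET-only focus is true NET. The reading chosen can change the main comparison.

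*Combined protocol and SAP*

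**What the plan says.** **Comparators.** Section 5.4 (Statistical Analysis) plans kappa statistics and McNemar's test on sensitivity and specificity for "PET-CT with SPECT and diagnostic CT for detecting NET".

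**Reference standard in 5.4.** Pathology comes first: "Results from pathology reports available from previous biopsy or surgical specimens will be considered the gold standard". Without it, "initial and follow up diagnostic CT or MRI scan following nonsurgical therapy including chemotherapy will be considered the gold standard". Nothing separates the CT under test from the CT that defines truth.

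**Lesion rules in 5.2 (Interpretation of Data).** One sentence makes cross-sectional imaging the check: "The presence of lesions will be confirmed by cross-sectional imaging of all patients with CT or MRI". The next covers lesions with "abnormal focal activity on Ga-68 PET images but not on morphologic images, such lesion/s will be considered positive NET". A third labels as positive for disease "Lymph nodes smaller than 1 cm on CT or MRI and showing marked avidity for" the tracer. For In-111 Octreotide the section adds that where such images "are available for comparison, the same imaging parameters will be applied".

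**A further confirmation rule.** Section 5.1.3 compares PET uptake with prior CT or MRI within 12 weeks to confirm lesions.

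**Who has pathology.** Criterion 3.5 admits patients "Histologically and/or clinically confirmed and/or suspicious of NET", so some lesions will have pathology and others will not. The documents do not give the share.

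**The concern.** The main objective is accuracy relative to conventional imaging, and that comparison turns on lesions that PET shows and CT does not. For such a lesion without pathology, the plan supports two scorings:

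- **5.2 as a truth rule.** The lesion is NET. It is a PET true positive and a CT miss, and can never be a PET false positive. This favours PET.
- **5.4 alone.** The lesion is not NET unless later CT or MRI shows it. Otherwise it is a PET false positive and a CT true negative. This favours CT, because the CT reading helps to define truth.

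No section says which applies, and no sensitivity analysis is planned. The same scans could therefore give different PET specificity and a different sensitivity result, and the choice could be made once results are known.

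**Working it through.** **Step 1: the plan's own figures.** Section 5.4 (Justification of Sample Size) expects 80 lesions, 60% positive: 48 positive, 32 negative. The 95% half-width at a proportion of 0.5 is 1.96 × √(0.25/n): 14.1 points (n=48), 17.3 (n=32) and 15.5 (n=40 patients). The plan states 14, 17 and 15, so they reproduce within rounding. The 48/32 split itself depends on how PET-only lesions are scored.

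**Step 2: illustrative inputs.** The 84-patient study in section 2.3 gives PET 69 TP and 2 FN (69/71 = 0.972), and CT 41 TP and 26 FN (41/67 = 0.612). These are patient-level rates, used here for lesions. I also assume conditional independence, no clustering and, for now, no false positives. Of 48 positives:

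- seen on both: 48 × 0.972 × 0.612 = 28.55
- PET only: 48 × 0.972 × 0.388 = 18.10
- CT only: 48 × 0.028 × 0.612 = 0.83
- neither: 0.52

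CT sees 29.37 and misses 18.63. As a check on independence, the study lists 26 CT misses and 2 CT-only true positives among its PET-CT discrepancies. Scaled by 48/67, these are 18.6 and 1.4, close to 18.10 and 0.83.

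**Step 3: 5.2 as a truth rule.** Reference positives = 28.55 + 18.10 + 0.83 = 47.5. CT sensitivity = 29.37/47.5 = 62%. Discordance is 18 v 1 for PET, exact two-sided p=0.00008.

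**Step 4: 5.4 alone.** Let v be the share of the 18.63 CT-missed lesions that pathology or follow-up verifies.

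- Reference positives = 29.37 + 18.63v
- CT sensitivity = 29.37/(29.37 + 18.63v)
- Sensitivity discordance, PET v CT = 18.10v v 0.83
- PET specificity = [32 + 0.52(1−v)]/[32 + 18.63(1−v)]

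| v | CT sensitivity | PET v CT discordance | exact p | PET specificity |
|---|---|---|---|---|
| 0 | 100% | 0 v 1 | 1.0 | 0.64 |
| 25% | 86% | 5 v 1 | 0.22 | 0.70 |
| 50% | 76% | 9 v 1 | 0.02 | 0.78 |
| 75% | 68% | 14 v 1 | 0.001 | 0.88 |

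PET sensitivity is 97% throughout.

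**Step 5: add false positives.** The same study gives CT 5 FP and 12 TN (5/17) and PET 1 FP and 12 TN; I take PET as 1/17 on the same base. On 32 negatives that is 9.41 for CT and 1.88 for PET, treated as falling on different lesions.

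- *Follow-up exposes them.* PET errors = 18.10(1−v) + 1.88, against 9.41 for CT. At v = 0, 25%, 50% and 75% this is 20 v 9, 15 v 9, 11 v 9 and 6 v 9; p = 0.06, 0.31, 0.82 and 0.61. No specificity difference is significant.
- *Follow-up does not expose them.* 5.4 counts the CT false positives as NET that PET missed. Sensitivity discordance, PET v CT, is then 0 v 10, 5 v 10, 9 v 10 and 14 v 10. PET leads only once v exceeds (0.83 + 9.41)/18.10 = 57%. At v = 0 the result favours CT (p = 2 × 0.5^10 = 0.002). The truth-rule result also weakens, to 18 v 10; twice the Binomial(28, 0.5) probability of 10 or fewer gives p=0.18.

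**Step 6: a check without the study's rates.** Take 48 lesions positive on the reference, all seen by CT, 2 of them missed by PET, and 10 PET-only foci among the other 32. Scored false: PET 46/48 = 95.8%, CT 48/48, p=0.50, PET specificity 22/32 = 68.8%. Scored true: PET 56/58 = 96.6%, CT 48/58 = 82.8%, 10 v 2, p=0.039.

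**The case against.** The strongest defence is that 5.2 only tells readers when to call a scan positive. Its heading, and the sentence applying the same parameters to In-111 Octreotide, point that way. This is a fair reading, but it does not remove the problem: 5.4 then governs alone, CT still helps to define its own truth, and unverified PET-only foci count against PET.

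A second defence is that the overlap is only partial, since pathology takes precedence and MRI or follow-up scans may decide. That stands. A reader might infer that CT sensitivity must be 100%; this happens only where the comparator CT reading alone is the reference, the v = 0 row.

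Three further inferences are tempting, and the documents do not support them:

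- *PET specificity is bound to be 100% if 5.2 is a truth rule.* The sentence covers only foci absent from morphologic images. Uptake at a CT-visible site can still be disproved.
- *PET leads on sensitivity under either reading.* That rests on assuming no false positives. With the cited study's CT false-positive rate, the lead can disappear or reverse (step 5).
- *PET would be significantly less specific under 5.4.* That rests on the same assumption and is lost once CT false positives are exposed.

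The numbers are also soft in general: patient-level rates from another study, used for lesions, clustering ignored, verified share unknown.

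**Conclusion.** The concern holds and should be settled before analysis. Followed as written, 5.4 leans towards CT. Reading 5.2 as a truth rule leans towards PET, and nothing in the plan chooses between them. Any unverified PET-only focus changes the size of the sensitivity gap and the PET specificity.

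Whether significance or direction also changes depends on quantities the documents do not give: the number of PET-only foci, the share verified, and how many CT false positives follow-up exposes. On the step 2 assumptions the contrast is 18 v 1 (p=0.00008) under the truth rule against 5 v 1 (p=0.22) under 5.4 with 25% verified. These figures show how far the choice can matter and do not predict this trial's result. Confidence is high in the conflict between the sections and limited in its magnitude.

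**What to change.** Reconcile 5.1.3, 5.2 and 5.4 into one reference standard:

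1. State that the 5.2 sentences on PET-only foci and on nodes under 1 cm are rules for calling the PET scan positive and do not define truth.
2. Name the comparator CT (the pre-study scan) and read it separately from the reference.
3. Take truth from pathology, or from later routine-care CT or MRI where available, never from the comparator CT or the study PET alone.
4. Keep all lesions in the analysis. Report PET sensitivity and specificity and both McNemar tests (CT and SPECT) with unverified PET-only lesions scored all true, then all false, and do the same for unverified CT-only or SPECT-only lesions.
5. Give the verified-lesion result as a supporting analysis. It should not be the main one: if 25% of lesions were verified, about 12 positives and 8 negatives would remain, with half-widths of 1.96 × √(0.25/n) = 28 and 35 points.
6. State as a limitation that later CT shares a modality with the comparator, so some lean towards CT remains.

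**Cost.** Amended wording, some chart abstraction into the CRF, a little more analysis, and a range in place of a single estimate. No scans or visits are added. Because the plan schedules only a 24-hour telephone call after imaging, the number of lesions with later scans is unknown, and the range may be wide.
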